5.3 Flowchart of the study cohort assembly

	Optum		Marketscan		Medicare*	
	Less Excluded Patients	Remaining Patients	Less Excluded Patients	Remaining Patients	Less Excluded Patients	Remaining Patients

All patients in the database		74,864,884		191,990,035		23,466,175
Patients who used exposure or a reference between 02 May 2011 to Dec 2017 (for Marketscan)/March 2019 (for Optum) and 01 January 2012-December 2017 for Medicare	-73,493,670	1,371,214	-190,287,730	1,702,305	-19,944,169	3,522,006
Patients who have continuous 6 months registration in the database	-185,581	1,185,633	-171,524	1,530,781	-972,275	2,549,731
Patients without prior use of reference	-877,495	308,138	-1,180,188	350,593	-1,838,491	711,240
Patients without prior use of exposure	-68,637	239,501	-59,423	291,170	-133,733	577,507
Excluded because patient qualified in >1 exposure category	-275	239,226	-211	290,959	-370	577,137
Patients who did not have missing age information	-12	239,214	0	290,959	0	577,137
Patients who did not have missing gender information	-19	239,195	0	290,959	0	577,137
Excluded based on Inclusion 1- DM Type 2	-18,341	220,854	-37,618	253,341	-10,507	566,630
Excluded based on Inclusion 5- Age >= 18	-19	220,835	-76	253,265	0	566,630
Excluded based on Inclusion 6- Body Mass Index (BMI) <= 45 kg/m2 at visit 1 (as a proxy, excluding patients with morbid obesity)	-9,096	211,739	-8,032	245,233	-13,155	553,475
Excluded based on Inclusion 8 - High risk of CV events	-64,122	147,617	-98,434	146,799	-67,114	486,361
Excluded based on Exclusion 1- Type 1 DM with ICD10 CODES	-2,983	144,634	-3,481	143,318	-12,175	474,186
Excluded based on Exclusion 2- Treatment (≥ 7 days) with GLP-1 RA, other DPP-4i or SGLT-2i	-7,712	136,922	-9,388	133,930	-23,347	450,839
Excluded based on Exclusion 3- Liver disease	-2,648	134,274	-1,931	131,999	-8,953	441,886
Excluded based on Exclusion 4- CKD Stage 5 (proxy for eGFR <15 ml/min/1.73 m2)/Dialysis	-707	133,567	-470	131,529	-3,368	438,518
Excluded based on Exclusion 5- Any history of or planned bariatric surgery	0	133,567	0	131,529	0	438,518
Excluded based on Exclusion 6- Previous cardiac procedure (CABG or PTCA or Stent) ≤ 2 months	-436	133,131	-569	130,960	-1101	437,417
Excluded based on Exclusion 8- Alcohol abuse/Drug abuse and Exclusion 10- Pregnancy	-1047	132,081	-501	130,459	-2,267	435,149

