6.3.1 Outcome variables

Effectiveness outcomes of interest (definitions provided in **Appendix A**):

- **Primary outcome:** 3-point major adverse cardiovascular events (MACE), i.e., non-fatal myocardial infarction, non-fatal stroke, or CV mortality
- Secondary outcomes: Individual MACE components:
 - Hospital admission for MI (for purposes of this individual component, fatal MI is included)
 - Hospital admission for stroke (for purposes of this individual component, fatal stroke is included)
 - All-cause mortality/CV mortality:
 - All-cause inpatient mortality identified using discharge status codes will be used as a proxy for “CV mortality” in commercial databases
 - Information on CV mortality through data linkage with the National Death Index (NDI) will only become available at a later date for Medicare and will be used in secondary analyses.

Control outcomes of interest (control outcomes only serve to assess aspects of study validity but are not further interpreted):

1. End Stage Renal Disease (we expect to see no association; Rosenstock et al., 2019)

Control outcome definitions

Outcome	Definition	Comments
Control Outcomes		
End Stage Renal Disease (ESRD)	
ESRD with dialysis, defined as:
 
An ICD9 diagnosis (inpatient or outpatient) for ESRD:
 
 ○ 585.5x, Chronic kidney disease, Stage V (for ESRD with no mention of dialysis) ○ 585.6x, End stage renal disease (for ESRD with dialysis) 
AND an ICD9 procedural codes for dialysis (=index date):
 
 ○ 39.95, Hemodialysis ○ 54.98, Peritoneal dialysis 
AND an additional procedural code for dialysis or physician provider code indicating dialysis procedure or ESRD-related activity within two time windows 31-60 and 61-90 days from index date. For patients who die prior to 61 days (31 days), the second (second and first) confirmation requirement(s) can be dropped. This ensures the inclusion of patients with true ESRD outcomes who die early (high early mortality) as well as early withdrawals from dialysis (which lead to high fatality within days or weeks).
	
Note- The corresponding ICD-10 codes will be used also

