
3) Active liver disease or impaired hepatic function, defined by serum levels of either ALT (SGPT), AST (SGOT), or alkaline phosphatase (AP) ≥ 3 x upper limit of normal (ULN) as determined at Visit 1.
	
Measured 180 days prior to drug initiation in any diagnosis/procedure position in inpatient or outpatient care setting:
 
Liver disease-ICD-9 diagnosis:
 
070.xx, 570.xx-573.xx 456.0x-456.2x, 576.8x, 782.4x, 789.5x
 
ICD-9 procedure codes:
 
39.1x, 42.91
	
Patorno, Elisabetta et al. "Cardiovascular outcomes associated with canagliflozin versus other non-gliflozin antidiabetic drugs: population based cohort study." BMJ 2018;360:k119 http://dx.doi.org/10.1136/bmj.k119
 
Patorno, Elisabetta et al. "Empagliflozin and the Risk of Heart Failure Hospitalization in Routine Clinical Care: A First Analysis from the Empagliflozin Comparative Effectiveness and Safety (EMPRISE) Study." Circulation. 2019 Apr 8. doi: 10.1161/CIRCULATIONAHA.118.039177

4) eGFR < 15 mL/min/1.73 m² (severe renal impairment or ESRD, MDRD formula), as determined during screening at Visit 1 and/or the need for maintenance dialysis.
	
Measured 180 days prior to drug initiation :
 
CKD stage 5 in any diagnosis/procedure position in inpatient or outpatient care setting- 585.5x OR
 
Dialysis in any diagnosis/procedure position and inpatient care setting:
 
Codes are in the sheet 'Dialysis' Sheet
	

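### As printed, Exclusion 4 misses outpatient dialysis coded 585.6x, so patients already on dialysis can enter and be counted as new events in the ESRD control outcome

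*Combined protocol and SAP*

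**What the plan says.** The CARMELINA criterion in the left column of Appendix A, Exclusion 4, covers very low eGFR "and/or the need for maintenance dialysis". The claims version beside it looks back 180 days and has two parts:

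- "CKD stage 5 in any diagnosis/procedure position in inpatient or outpatient care setting- 585.5x OR"
- "Dialysis in any diagnosis/procedure position and inpatient care setting", pointing to the Dialysis sheet later in Appendix A.

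The Section 5.3 flowchart labels the step "Excluded based on Exclusion 4- CKD Stage 5 (proxy for eGFR <15 ml/min/1.73 m2)/Dialysis" and states no care setting.

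Section 6.3.1 defines the ESRD control outcome. It starts from "An ICD9 diagnosis (inpatient or outpatient) for ESRD", with two qualifying codes. One is 585.5x, labelled as carrying no mention of dialysis. The other is "585.6x, End stage renal disease (for ESRD with dialysis". The event is dated by a procedure code, 39.95 or 54.98: "AND an ICD9 procedural codes for dialysis (=index date". Confirmation is then required in two later windows, relaxed for early death. A kidney transplant code is a separate route to the outcome.

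**The concern.** The part of Exclusion 4 that reads outpatient claims uses the code which the protocol itself labels as not mentioning dialysis. The part that looks for dialysis is limited to inpatient care. The code labelled for end-stage disease on dialysis is in neither part. The patient whom the trial criterion targets, someone established on maintenance dialysis outside hospital, is therefore the one whom the printed rule can miss.

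Such a patient is a prevalent case, and the outcome definition has nothing further to stop that patient being counted as incident. ESRD is the study's only control outcome, with no association expected. Prevalent cases counted as events would pull a real difference towards the null if they were equally common in the two arms, and could produce a false difference if they were not. At stake are the value of that check and fidelity to the criterion being emulated.

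**Working it through.** **1. The plan's own figures for this step (Section 5.3).** The subtractions reproduce exactly.

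- Optum: 134,274 − 707 = 133,567; 707 / 134,274 = 0.53%.
- MarketScan: 131,999 − 470 = 131,529; 470 / 131,999 = 0.36%.
- Medicare: 441,886 − 3,368 = 438,518; 3,368 / 441,886 = 0.76%.
- Together: 707 + 470 + 3,368 = 4,545, of 134,274 + 131,999 + 441,886 = 708,159, which is 0.64%.

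The flowchart does not separate 585.5x from dialysis. These counts are a baseline for a re-run and do not estimate the patients retained.

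**2. Code lists.** The outcome's list of confirming codes (Section 6.3.1) and the Dialysis sheet (Appendix A) each hold 2 ICD-9 procedure, 3 ICD-9 diagnosis, 22 CPT and 13 HCPCS codes: 2 + 3 + 22 + 13 = 40. They share 39. Only the outcome list has 585.6x, and only the sheet has V45.1x. The sheet includes home and outpatient services (99512, G0257, S9335, S9339), which fit poorly with an inpatient filter.

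**3. Baseline protection.** Sections 6.3.1 and 6.3.2 require no period free of ESRD, dialysis or transplant, and do not require the qualifying dialysis code to be the first. Section 13.1 computes the hazard ratio for each outcome in the same matched cohort. Exclusion 4 is therefore the only baseline protection, and it does not cover a prior transplant.

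**4. The route, condition by condition.** To enter, a patient on outpatient or home dialysis must:

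- carry 585.6x and not 585.5x in the 180 days;
- have no inpatient Dialysis-sheet code in those 180 days;
- meet Inclusion 8, whose macrovascular routes as implemented set no renal limit.

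To be counted, the patient must then have 39.95 or 54.98 (or the ICD-10 equivalent) recorded in follow-up with the required confirmation, or a transplant code. Among the dialysis codes, only those two procedures can date an event. 585.6x can supply the qualifying diagnosis and can also confirm.

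**5. Time for this to happen.** Section 9 gives median follow-up by arm of 122 and 118 days (Optum), 148 and 127 (MarketScan) and 148 and 127 (Medicare), and 57.74% of follow-up ended with the index exposure. The ITT analysis is capped at 365 days (Section 6.3.2). This limits the number of such events but does not make it zero.

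**6. Direction only, with every input assumed.** Let r be the true incident ESRD risk (0.1 to 0.3%), q the retained prevalent dialysis in the referent arm (0.05 to 0.5%) and f the fraction of these meeting the outcome (25 to 75%). None of these comes from the documents.

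- Prevalent share of referent events = qf / (r + qf). Low: 0.000125 / 0.003125 = 4%. High: 0.00375 / 0.00475 = 79%.
- True risk ratio 1.5, equal q in both arms: (1.5r + qf) / (r + qf). Low contamination: 0.004625 / 0.003125 = 1.48. High: 0.00525 / 0.00475 = 1.11.
- True null, q higher by a factor k in the linagliptin arm: (r + kqf) / (r + qf). With k = 1.25 at the low end: 0.00315625 / 0.003125 = 1.01. With k = 1.5 at the high end: 0.006625 / 0.00475 = 1.39.

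The width of these ranges shows that the size depends entirely on figures the documents do not give.

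**The case against.** The strongest reply is that the inpatient wording may be a drafting slip. The flowchart label gives no setting, the sheet lists home services, the ICD-10 lists are held outside the document, and the Dialysis row of Table 1 is zero in both arms and all databases, before and after matching. The restriction could also be deliberate, since Appendix A limits setting for some other codes. Either is possible. But the Table 1 row states no codes, setting or window, and would also read zero if built with the same inpatient filter. It settles nothing either way.

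A second reply is that matched renal covariates are close: CKD 34.5% against 34.9%, CKD stage 3-4 28.0% against 28.0%. That is reassuring, but Table 1 has no separate ESRD row, so balance on prevalent ESRD cannot be seen.

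A third is that little hangs on this outcome: Section 6.3.1 says "control outcomes only serve to assess aspects of study validity but are not further interpreted". That stands, and it limits the harm to the validity check.

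A reader might infer more than the text supports:

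- That dialysis patients were in fact retained. The documents do not show what was programmed.
- That the ESRD outcome has no baseline exclusion at all. Exclusion 4 is a cohort-wide 180-day one, applied before matching; it is incomplete as printed.
- That the primary result is biased. Nothing in the documents supports this.

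**Conclusion.** The point holds as a statement about the printed rules, and it is minor. Exclusion 4 as written does not fully implement the maintenance-dialysis criterion, and it is the only baseline safeguard for the ESRD control outcome. Following the text can admit a prevalent dialysis patient and count that patient as a new ESRD event.

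The number affected cannot be derived, and the route is narrow given the coding conditions and median as-treated follow-up of 118 to 148 days by arm. The conclusion assumes that the program follows the print and that the external ICD-10 lists mirror the printed ICD-9 ones. If either assumption fails, part or all of the setting and code-list problem becomes a text correction. The lack of any transplant restriction for the outcome would remain.

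**What to change.** 1. Compare the programmed Exclusion 4 with Appendix A.
2. If it matches the print, apply 585.5x, 585.6x, their ICD-10 equivalents and the Dialysis-sheet codes in inpatient or outpatient care over the existing 180 days. Re-run the flowchart and the match, and report removals by arm and database beside the current 707, 470 and 3,368.
3. If it does not match the print, correct the text to state the codes and settings actually used.
4. In the ESRD control-outcome analysis, do not count as events patients with an ESRD, dialysis or transplant code in the same 180 days, and report how many there are by arm. Once Exclusion 4 is corrected, this mainly adds prior transplant.
5. Optionally, repeat that analysis with all available look-back as a sensitivity analysis. Its length will differ between patients, because only 180 days of enrolment is required.
6. State the codes, setting and window behind the Table 1 Dialysis row.

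The cost is a program check, a text or code-list edit and one restriction in one analysis. The flowchart and match are re-run only under step 2, probably with a small loss of patients, though the documents give no number. The date and report fields in Section 13 are blank in this version, so the change can be made before any hazard ratio is reported.

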Appendix A

	
5) Any previous (or planned within next 12 months) bariatric surgery (open or laparoscopic) or intervention (gastric sleeve).
	
Measured 180 days prior to drug initiation in any procedure position in inpatient or outpatient care setting: Any history CPT-Code-Abbreviation Procedure 43644 -LRYBG- Laparoscopic Roux-en-Y gastric bypass (Roux limb 150 cm or less) 43645 -LRYGBX- Laparoscopic gastric bypass with small intestine reconstruction to limit absorption 43770 -LAGB- Laparoscopic adjustable gastric band 43846 -ORGB- Open Roux-en-Y gastric bypass (Roux limb 150 cm or less) 43847 -ORGBX- Open gastric bypass with small intestine reconstruction to limit absorption
	
Patorno, Elisabetta et al. "Cardiovascular outcomes associated with canagliflozin versus other non-gliflozin antidiabetic drugs: population based cohort study." BMJ 2018;360:k119 http://dx.doi.org/10.1136/bmj.k119
 
Patorno, Elisabetta et al. "Empagliflozin and the Risk of Heart Failure Hospitalization in Routine Clinical Care: A First Analysis from the Empagliflozin Comparative Effectiveness and Safety (EMPRISE) Study." Circulation. 2019 Apr 8. doi: 10.1161/CIRCULATIONAHA.118.039177

	
6) Pre-planned coronary artery re-vascularization (PCI, CABG) or any previous PCI and/or CABG \leq 2 months prior informed consent
	
Measured 60 days prior to drug initiation in any diagnosis position and procedure position in care settings indicated below: (\leq 2 months) PTCA: Inpatient CPT-4: 92973, 92982, 92984, 92995, 92996, 92920 – 92921, 92924 – 92925, 92937, 92938, 92941, 92943, 92944 OR – Inpatient or outpatient: ICD-9 procedure: 00.66, 36.01, 36.02, 36.03, 36.05, 36.09
 
Stenting: Inpatient CPT-4: 92980, 92981, 92928 – 92929, 92933 - 92934 OR – Inpatient or outpatient ICD-9 procedure: 36.06, 36.07
 
CABG: Inpatient CPT-4: 33510 – 33536, 33545, 33572. OR – Inpatient or outpatient ICD-9 procedure: 36.1x, 36.2x
	
Patorno, Elisabetta et al. "Cardiovascular outcomes associated with canagliflozin versus other non-gliflozin antidiabetic drugs: population based cohort study." BMJ 2018;360:k119 http://dx.doi.org/10.1136/bmj.k119
 
Patorno, Elisabetta et al. "Empagliflozin and the Risk of Heart Failure Hospitalization in Routine Clinical Care: A First Analysis from the Empagliflozin Comparative Effectiveness and Safety (EMPRISE) Study." Circulation. 2019 Apr 8. doi: 10.1161/CIRCULATIONAHA.118.039177

	
7) Known hypersensitivity or allergy to the investigational products or its excipients.
	N/A	-
	
8) Any previous or current alcohol or drug abuse that would interfere with trial participation in the opinion of the investigator.
	
Measured 180 days prior to drug initiation in any diagnosis position in inpatient or outpatient care setting: Alcohol abuse or dependence 291.xx, 303.xx, 305.0x, 571.0x, 571.1x, 571.2x, 571.3x, 357.5x, 425.5x, E860.0x, V11.3x Drug abuse or dependence 292.xx, 304.xx, 305.2x-305.9x, 648.3x
	
Patorno, Elisabetta et al. "Cardiovascular outcomes associated with canagliflozin versus other non-gliflozin antidiabetic drugs: population based cohort study." BMJ 2018;360:k119 http://dx.doi.org/10.1136/bmj.k119
 
Patorno, Elisabetta et al. "Empagliflozin and the Risk of Heart Failure Hospitalization in Routine Clinical Care: A First Analysis from the Empagliflozin Comparative Effectiveness and Safety (EMPRISE) Study." Circulation. 2019 Apr 8. doi: 10.1161/CIRCULATIONAHA.118.039177

	
9) Participation in another trial with an investigational drug ongoing or within 2 months prior to visit 1 (screening)*.
	N/A	-
	
9) Participation in another trial with an investigational drug ongoing or within 2 months prior to visit 1 (screening)*.
	
Measured 180 days prior to drug initiation in any diagnosis/procedure position in inpatient or outpatient care setting: Please see Pregnancy codes sheet.
	
	
11) Patients considered unreliable by the investigator concerning the requirements for follow-up during the study and/or compliance with study drug administration, have a life expectancy less than 5 years for non-CV causes, or have cancer other than non-melanoma skin cancer within last 3 years, or has any other condition than mentioned which in the opinion of the investigator, would not allow safe participation in the study.
	
Measured over 365 days prior to drug initiation: CCI \geq10 OR
 
Measured 1095 days prior to drug initiation in any diagnosis position in inpatient and outpatient care setting: History of malignant neoplasm ICD-9: 140.xx-208.xx (except 173.xx, non-melanoma skin cancer)- in prior 3 years
	
"Gagne, Josh J et. al. ""A combined comorbidity score predicted mortality in elderly patients better than existing scores." J Clin Epidemiol. 2011 Jul;64(7):749-59. doi: 10.1016/j.jclinepi.2010.10.004.
 
Sun, Jenny W et. al. ""Validation of the Combined Comorbidity Index of Charlson and Elixhauser to Predict 30-Day Mortality Across ICD-9 and ICD-10." Med Care. 2018 Sep;56(9):812. doi: 10.1097/MLR.0000000000000954."

	
12) Acute coronary syndrome (ACS), diagnosed \leq 2 months prior to visit 1 (screening).
	
Measured 60 days prior to drug initiation in any diagnosis position in inpatient and outpatient care setting: ACS/unstable angina 411.xx
	
Patorno, Elisabetta et al. "Cardiovascular outcomes associated with canagliflozin versus other non-gliflozin antidiabetic drugs: population based cohort study." BMJ 2018;360:k119 http://dx.doi.org/10.1136/bmj.k119
 
Patorno, Elisabetta et al. "Empagliflozin and the Risk of Heart Failure Hospitalization in Routine Clinical Care: A First Analysis from the Empagliflozin Comparative Effectiveness and Safety (EMPRISE) Study." Circulation. 2019 Apr 8. doi: 10.1161/CIRCULATIONAHA.118.039177

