Ib	Advanced coronary artery disease, defined by any one of the following: • ≥ 50% narrowing of the luminal diameter in 2 or more major coronary arteries by coronary angiography, MRI angiography or CT angiography; Definition of major coronary arteries: LAD (Left Anterior Descending), CX (Circumflex) or RCA (right coronary artery) • Left main stem coronary artery with ≥ 50% narrowing of the luminal diameter by coronary angiography, MRI angiography or CT angiography; • Prior percutaneous or surgical revascularization of ≥ 2 major coronary arteries at least 2 months prior to Visit 1 (screening); • The combination of prior percutaneous or surgical revascularization of 1 major coronary artery at least 2 months prior to visit 1 (screening), and ≥ 50% narrowing of the luminal diameter by coronary angiography, MRI angiography or CT angiography of at least 1 additional major coronary artery.	Ischemic heart disease in any diagnosis position and inpatient or outpatient care setting: ICD-9 410.xx-414.xx OR Previous cardiac procedure (CABG or PTCA or Stent) in any procedure position and care setting defined below: PTCA: Inpatient CPT-4: 92973, 92982, 92984, 92995, 92996, 92920 – 92921, 92924 – 92925, 92937, 92938, 92941, 92943, 92944 OR – Inpatient or outpatient ICD-9 procedure: 00.66, 36.01, 36.02, 36.03, 36.05, 36.09 Stenting: Inpatient CPT-4: 92980, 92981, 92928 – 92929, 92933 - 92934 OR – Inpatient or outpatient ICD-9 procedure: 36.06, 36.07 CABG: Inpatient CPT-4: 33510 – 33536, 33545, 33572. OR – Inpatient or outpatient ICD-9 procedure: 36.1x, 36.2x Transmyocardial revascularization: Inpatient or Outpatient CPT-4: 33140, 33141 OR -Inpatient or outpatient ICD-9 procedure: 36.31-36.34	Patorno, Elisabetta et al. "Cardiovascular outcomes associated with canagliflozin versus other non-gliflozin antidiabetic drugs: population based cohort study." BMJ 2018;360:k119 http://dx.doi.org/10.1136/bmj.k119 Patorno, Elisabetta et al. "Empagliflozin and the Risk of Heart Failure Hospitalization in Routine Clinical Care: A First Analysis from the Empagliflozin Comparative Effectiveness and Safety (EMPRISE) Study." Circulation . 2019 Apr 8. doi: 10.1161/CIRCULATIONAHA.118.039177

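### As printed, Exclusion 6 reads the PTCA and stent CPT-4 codes in inpatient care only, so a PCI within 60 days recorded only by CPT-4 in outpatient care is not excluded

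*Combined protocol and SAP*

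**What the plan says.** In Appendix A, Exclusion criterion 6, the trial column bars "any previous PCI and/or CABG" in the 2 months before consent, with no mention of care setting. The claims column sets the look-back and leaves the setting to each code list: "Measured 60 days prior to drug initiation in any diagnosis position and procedure position in care settings indicated below".

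Each PCI list then has two limbs joined by OR:

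- **PTCA, CPT-4:** "PTCA: Inpatient CPT-4: 92973, 92982, 92984, 92995, 92996" and further codes, inpatient only.
- **PTCA, ICD-9 procedure:** "OR – Inpatient or outpatient: ICD-9 procedure: 00.66, 36.01, 36.02, 36.03, 36.05, 36.09".
- **Stent, CPT-4:** "Stenting: Inpatient CPT-4: 92980, 92981" and further codes, inpatient only.
- **Stent, ICD-9 procedure:** "OR – Inpatient or outpatient ICD-9 procedure: 36.06, 36.07".

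Inclusion 8 Ib carries the same inpatient label on the PTCA and stent CPT-4 codes, but reads the transmyocardial revascularization codes more widely: "Inpatient or Outpatient CPT-4: 33140, 33141". Exclusion 5, directly above Exclusion 6, reads its bariatric CPT codes in inpatient or outpatient care. Appendix A also states that the ICD-10 lists are kept outside the document. Section 5.2.2 says the criteria follow the trial as nearly as the data allow.

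**The concern.** The trial excluded recent PCI wherever it was done. As printed, whether the emulation excludes it can depend on where the claim was recorded and in which code system. A patient whose recent stent appears as an inpatient CPT-4 code leaves the cohort. A patient whose stent appears only as an outpatient CPT-4 code stays.

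The same inpatient limit does little harm in Inclusion 8 Ib. There, an ischemic heart disease diagnosis (ICD-9 410 to 414) in inpatient or outpatient care is enough for this part of the criterion. Exclusion 6 has no diagnosis limb to fill the gap. A patient can therefore meet the coronary part of Inclusion 8 on an outpatient diagnosis while the outpatient PCI goes unseen.

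At stake is fidelity to one trial exclusion, not the main result.

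**Working it through.** **Step 1. Set the rules side by side.** Take a PCI within 60 days of drug initiation.

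| How the PCI is recorded | Trial rule | Exclusion 6 as printed |
|---|---|---|
| Inpatient, listed CPT-4 | excluded | excluded |
| Inpatient, listed ICD-9 procedure | excluded | excluded |
| Outpatient, listed ICD-9 procedure | excluded | excluded |
| Outpatient, CPT-4 only | excluded | not excluded |

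Only the last row differs.

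**Step 2. Could another criterion catch the last row?** Exclusion 12 reads ICD-9 411.xx in the same 60 days, in inpatient and outpatient care. It would remove those who also carry a 411.xx code. A PCI without one passes.

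**Step 3. Reproduce the flowchart at this step (Section 5.3).**

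- Optum: 133,567 − 436 = 133,131; 436/133,567 = 0.33%.
- MarketScan: 131,529 − 569 = 130,960; 569/131,529 = 0.43%.
- Medicare: 438,518 − 1,101 = 437,417; 1,101/438,518 = 0.25%.
- Total: 2,106/703,614 = 0.30%, leaving 703,614 − 2,106 = 701,508.

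The remaining counts match those printed. The row covers CABG, PTCA and stents together, so 2,106 is not a count of inpatient PCI. It also includes any outpatient PCI caught by ICD codes.

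**Step 4. Size of the missed group, by assumption only.** The documents do not say how often an outpatient PCI carries only a CPT-4 code. Let the missed number be m times the 2,106 caught.

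- m = 0.25: about 530 patients; 526.5/701,508 = 0.08%.
- m = 1: 2,106 patients; 2,106/701,508 = 0.30%.
- m = 2: about 4,210 patients; 4,212/701,508 = 0.60%.

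To reach 1% of those remaining (about 7,015 patients), m would have to be 7,015/2,106 = 3.3. If the missed patients were spread evenly over the 101,830 matched patients (2 × 50,915), the range is 101,830 × 526.5/701,508 = 76 to 101,830 × 4,212/701,508 = 611.

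**Step 5. Effect on the hazard ratio.** If a fraction f of one arm has k times the event rate of the rest, that arm's rate is multiplied by about 1 + f(k − 1). Suppose f = 0.0060 in one arm and none in the other, with k = 2 (an assumption). The ratio then moves by a factor of 1 + 0.0060 × 1 = 1.006. With equal fractions and rates in both arms the shift cancels.

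**The case against.** The setting is stated list by list, so the inpatient label may be a deliberate choice. It is used for the same codes in Inclusion 8 Ib, and published cohort definitions are cited beside it. The transmyocardial codes are for a different procedure and do not prove that the PCI label is a slip. This stands as a reason to ask whether the limit is intended. It does not change which patients the printed rule misses, and no reason for the difference is given.

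Three stronger readings are tempting, and the documents do not support them:

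- **That every recent outpatient angioplasty or stent stays in.** The OR limb excludes any that carries a listed ICD-9 procedure code, and the unprinted ICD-10 lists may catch more.
- **That many patients are wrongly kept.** This needs two facts that the documents do not give: that outpatient PCI in these databases is recorded by CPT alone, and what share of PCI is outpatient. An assumed outpatient share s in 2,106 × s/(1 − s) also treats all 2,106 exclusions as inpatient PCI, which the row label contradicts.
- **That the propensity score cannot balance the missed patients.** The code list behind the Previous cardiac procedure covariate is not printed. Matched Table 1 also balances the broader History of CABG or PTCA (4,608, 9.1%, against 4,561, 9.0%), ischemic heart disease (39.9% against 39.8%) and cardiologist visits in the prior 30 days (13.8% against 13.9%). Nothing in the documents suggests that the gap differs by arm.

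**Conclusion.** The point holds in a narrow form. As printed, Exclusion 6 does not remove a PCI within 60 days that is recorded only by CPT-4 in outpatient care, although the trial rule would remove it. This follows from the text alone and needs no assumption.

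Its size does not follow from the documents. Over the assumed range of 0.25 to 2 times the patients caught, the missed group is 0.08% to 0.60% of those remaining after the step, before any removal by Exclusion 12. It would stay below 1% unless the missed patients exceeded three times all those caught. The effect on the hazard ratio should be very small. Severity is minor: the change brings one exclusion closer to the rule it is meant to copy and is not expected to alter the conclusion.

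**What to change.** In Exclusion 6, read the PTCA and stent CPT-4 codes already listed in inpatient or outpatient care. Report the added exclusions for each database, and rerun the flowchart step and the propensity-score match before the Section 13 comparative analysis, which carries no completion date in this document. If the Previous cardiac procedure covariate uses the same code list, apply the same setting there. If the inpatient limit is intended, state the reason in Appendix A and give the count of outpatient CPT-only PCIs within 60 days.

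The cost is one filter change, a cohort rerun with refreshed balance and power tables (Sections 9 and 10), and a very small loss of patients.
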